3.1 STUDY POPULATION

3.2 Description and source of study population and catchment area: We will recruit HIV-positive YBMSM from clinical, research and community settings. Flyers will be posted for self-referral in the Grady IDP clinic, community-based organizations, and other venues (e.g. coffee shops) as directed by our YCAB (Example in Appendix H: final version will be created with YCAB input). Additionally, participants may be referred from other studies. Participants will be residents of the greater Atlanta area—with no strict boundaries provided they are able to get back and forth from their homes to the intervention sites in Midtown Atlanta.

3.3 Inclusion and Exclusion criteria:

3.2.1 Inclusion Criteria (participants):

- Age \leq 29 years and \geq 18 years
- Self-identify as Black/African-American (inclusive of multiracial identities)
- Male sex at birth
- Endorse history of sex with men ever (inclusive of gay and bisexual men)
- HIV-positive (self-reported by participant and confirmed by medical record)
- Able and willing to provide written consent and participate in surveys, interviews, and/or group intervention

3.2.2 Inclusion Criteria (key informants):

- Experience working with YBMSM in clinical or CBO settings
- Able and willing to provide verbal consent and participate in in-depth interviews

3.2.3 Exclusion Criteria

- Age $<$ 18 years or \geq 30 years
- Unwilling or unable to provide written informed consent
- Enrollment in one phase of the study is an exclusion criteria for enrollment in other phases

3.3 Justification for inclusion/exclusion criteria: We are focusing exclusively on YBMSM in this study due to the disproportionate impact of HIV in this population, as detailed in the literature review above. We are aiming to develop an intervention that is culturally and developmentally appropriate, and as such are limiting our enrollment to this target population.

3.4 Estimated number of participants: We plan to enroll 180 total participants (120 in the randomized controlled trial and 60 in preliminary interviews).

3.5 Sampling, including sample size and statistical power:

Based on our MSCS scale characteristics in our previous online survey study (mean 26.6, standard deviation 7.0), we can estimate that a sample size of n=106 (n=53 in each of the intervention and control groups) would allow us to detect approximately a 15% increase in social capital attributable to our intervention (using 80% statistical power). For the RCT, we will therefore aim to recruit n=120 patients (accounting for some attrition): based on our team's previous work in the same geographic area, we believe this to be a feasible number of YBMSM to recruit during the specified time period from our IDP clinic and community partners.

Table 1. Power calculation

Control Patients	Intervention Patients	Control SC Mean	Intervention SC Mean	Detectable Effect Size	Detectable Percent Increase in SC
31	31	26.6	31.9	0.75	20%
39	39	26.6	31.3	0.67	17.5%
50	50	26.6	30.7	0.58	15.4%
53	53	26.6	30.6	0.57	15%
77	77	26.6	29.9	0.47	12.5%
114	114	26.6	29.3	0.38	10%

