1.5.1 Aims and Hypothesis

Aim 1: To characterize the social networks of YBMSM living with HIV with respect to the multiple dimensions of social capital using a mixed-methods research design.

Aim 2: To develop a social capital-based intervention to enhance engagement in care among HIV-positive YBMSM utilizing a participatory, youth-centered approach.

[figure not shown]
Aim 3: Implement a randomized controlled trial with groups of HIV-positive YBMSM to develop and pilot our social capital interventions.

Aim 3a: To assess participant satisfaction and feasibility of the intervention.

Aim 3b: To test impact on social capital and HIV care engagement outcomes.

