2.0 PROCEDURES/METHODS: Design

Figure 3. Study Design*

*We envision each arm in Phase II will have six groups of approximately 10 participants, completing the same intervention or H4L curriculum.

As depicted in Figure 3 above, there are three phases of our research, each corresponding to one of the study aims: **Phase I: a mixed methods exploration of social capital and development of a social capital intervention; Phase II: a randomized controlled trial of the social capital intervention; and Phase III: 1-, 4-, and 10-month follow up for the RCT.** For Phase I, we will recruit 30 HIV-positive YBMSM and explore the nature of their social capital and social networks using in-depth individual qualitative interviews (IDIs). We will also analyze previously collected survey data (from a pilot study of 80 YBMSM, conducted last year) to quantitatively understand relationships between social capital constructs and engagement in care. We will also engage 30 key informants (healthcare providers and community-based organization (CBO) staff) in IDIs to gain their input about how best to augment social capital among YBMSM. We will use the information collected in the formative research, and together with a Youth Community Advisory Board (Y CAB), we will develop an intervention to augment social capital among YBMSM. In Phase II, we will conduct an RCT with 120 YBMSM, split between 6 intervention groups and 6 control groups. Groups in each arm will implement the same intervention (social capital intervention arm) or receive the same health education information (H4L). Justification for the number of groups is provided below. Finally, in Phase III, we will obtain follow-up data at 3 and 9 months after study completion.

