2.3 Procedure: Phase II and III (Aim 3- Randomized Controlled Trial) (n=120)

Randomized Controlled Trial Overview: We propose a prospective RCT in which groups of YBMSM will implement a novel intervention with the goal of enhancing social capital and engagement in care among YBMSM living with HIV. Sixty of our participants will be randomized to the treatment arm (divided into at least 6 groups) and participate in the social capital intervention, while the other 60 will be randomized to a group-based health promotion intervention (divided into at least 6 groups) that does not explicitly aim to build social capital (Health for life, or “H4L”). (See Figure 3) Each of the 6 groups in the treatment arm will implement the same intervention. Six groups are necessary in order to ensure that each group has no more than 10 individuals, ensuring that groups are neither too small nor too big. Each of the 6 groups in the group-based health promotion intervention arm will also complete the same curriculum. We will measure social capital using our Modified Social Capital Scale (MSCS; Appendix F, Section 2) at baseline, immediately after completing the intervention (approximately 1 month) and at 4 and 10 months after beginning the intervention. We will also abstract clinical data from electronic medical records at these time points in order to quantify any effect on our care engagement outcomes.

Overview--Intervention Arm: The social capital intervention will be implemented according to the detailed guidelines and manual developed in Phase I above. We will plan for our intervention (and our control condition) to be delivered in either a one day or consecutive two day group meeting at Emory University Rollins School of Public Health or another agreed upon location, at mutually convenient times for the participants. Staff members will be flexible in case evening or weekend meeting times are more convenient for the study participants. The exact number of sessions and

format of the intervention may be modified based on YCAB input; it may be that the intervention can be delivered in fewer sessions, or in a retreat format, to enhance acceptability and retention.

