Community Photovoice Project: Our social capital intervention will focus on developing skills and group-work that culminate in participant-derived ***photovoice projects***. This is based on our own and others' prior qualitative work that demonstrates HIV-positive YBMSM's interest in HIV education, peer mentoring, and community involvement.^{48,49} We envision having six sets of intervention and control groups with 10 YBMSM in each group (Figure 3). *Each group of YBMSM will be encouraged to complete a 30 day photovoice challenge.* The 30 day challenge is based on a prior community action project done as a part of our CFAR-funded research, which was a Photovoice project conducted by [name] and an MPH student.⁵⁰ Photovoice is a participatory action research methodology in which groups of individuals from a population of interest are given cameras to document events, people and places of significance in their lives.⁵¹ In that project, n=7 YBMSM were recruited from AID Atlanta (one of our CBO partners) and given digital cameras with which to document and describe events, people and places of significance in their lives. Their pictures and the ensuing discussions gave us insight into community and identity within the population. Costs included digital cameras, compensation for transportation to meetings, and printing of photos for display in a booklet and a community exhibit.

As we saw preliminarily with our Photovoice experience, we expect that the process of working together with other YBMSM and engaging the community will enhance the social capital of individuals in the intervention arm by creating bonds that will lead to the aforementioned health-promoting mechanisms: informational support, emotional support, instrumental support and collective efficacy (Figure 2).

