Again, the exact nature of the 30 day challenge and the intervention will be determined in conjunction with the YCAB over the course of Phase I intervention development. (The control groups will not participate in the 30 day challenge). The process of working on the 30 day challenge as part of the proposed social capital intervention has the potential to increase bonding social capital through the group's interactions with one another, as well as bridging social capital through meaningful connections with community partners and study staff. Finally, the act of creating and executing a community-oriented project will also increase participants' sense of collective efficacy (as measured by items in the MSCS), another important component of social capital.

Overview--Control arm: The control arm will participate in a health education intervention that will be delivered in a group, but without a specific goal of creating group cohesion or social capital. The intervention will be a modified version of "Health for Life" or H4L, which was used as a control arm intervention in a recently completed protocol of the Adolescent Trials Network which was co-chaired by [name] (University of Michigan). This intervention was specifically developed for young MSM of color and focuses on general health topics including diet, exercise, and safe sex. Details about the Health for Life program are included as Appendix G. We will modify the H4L intervention as needed based on the input of our YCAB. Similar to the intervention arm, the control participants will participate in either a one day or a consecutive two day group meeting at a convenient time and location. The exact number of sessions and format of

the intervention may be modified based in YCAB input; as with the intervention arm--it may be that the intervention can be delivered in fewer sessions, or in a retreat format, to enhance acceptability and retention. The same format and number of sessions will be used for both the intervention and control arms.

Procedures for intervention and control participants:

Tokens of appreciation: We will provide participants with two gift cards (value \$75) as a token of appreciation for their time and will also provide Metropolitan Atlanta Rapid Transit Authority passes (MARTA cards; \$5 fare for a single round-trip) if needed for transportation assistance. \$25 will be given on the first day and \$50 will be given on the second day

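### The 80% power claim in Section 3.5 treats participants as independent, although both arms are delivered in about six groups of ten and no ICC or group-aware arm comparison is stated

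*Combined protocol and SAP*

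**What the plan says.** Section 3.5 takes a control mean of 26.6 and an SD of 7.0 from an earlier online survey and states that 106 participants (53 per arm) "would allow us to detect approximately a 15% increase in social capital attributable to our intervention (using 80% statistical power"). Recruitment is then raised: "we will therefore aim to recruit n=120 patients (accounting for some attrition"). Table 1 lists per-arm sizes against detectable effects. Neither the text nor the table gives alpha, the test, an ICC or a design effect.

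Delivery is in groups. The note to Figure 3 in Section 2.0 says "We envision each arm in Phase II will have six groups of approximately 10 participants", and Section 4.3 repeats six groups per arm. Section 2.3 has participants allocated first and grouped afterwards: "Sixty of our participants will be randomized to the treatment arm (divided into at least 6 groups"), with the same arrangement for control. Section 2.0 promises a justification for the number of groups. The one given in Section 2.3 concerns group size only: "Six groups are necessary in order to ensure that each group has no more than 10 individuals".

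Section 2.3 also describes the mechanism. Working together "will enhance the social capital of individuals in the intervention arm by creating bonds", and the 30-day challenge "has the potential to increase bonding social capital through the group's interactions with one another". The control curriculum is delivered in groups too, but has no cohesion goal.

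Aim 3b is "To test impact on social capital and HIV care engagement outcomes". Section 5.2.1 compares social capital between engaged and non-engaged patients. It contains no comparison of MSCS between the randomized arms.

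**The concern.** Randomizing individuals does not remove correlation that arises after allocation. If some groups bond better than others, the follow-up MSCS scores of people in the same group will be alike, and 53 people in six groups carry less information than 53 independent people. The outcome is the construct that group interaction is meant to change, so a zero ICC needs a reason, at least in the intervention arm. In the control arm the correlation may be weaker or absent.

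Two things are at stake. The stated power may be too high for any analysis that respects the groups. And because no between-arm analysis is written down, nothing prevents the use of a test that ignores the groups, which would have inflated type I error.

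**Working it through.** **Inputs from the plan.** Mean 26.6, SD 7.0 (variance 49), 53 per arm, 6 groups per arm, difference 0.15 × 26.6 = 3.99.

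**Assumed, because the plan does not give them.** Two-sided alpha 0.05; ICC 0.02 to 0.10; correlation r between baseline and follow-up MSCS of 0.3 to 0.7, with 0.5 as the central value.

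**1. The plan's own figure.** For independent participants, 80% power needs 49 per arm (normal approximation) or 50 (t-test). At 53 per arm the t-test has power 0.83. A rank-test allowance gives 50 × π/3 = 52.4, rounded up to 53, so Table 1 is explained without any clustering term. Even if the whole excess over 49 were a hidden design effect, 53/49 = 1.08 would cover an ICC of only 0.08/9 ≈ 0.009 with groups of 10.

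**2. The attrition allowance has no spare room.** The step from 106 to 120 allows for 1 − 106/120 = 11.7% loss. The 87% retention cited in Section 2.3 would leave 0.87 × 120 ≈ 104.

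**3. Power for a group-aware, baseline-adjusted comparison.** Variance of an arm mean:

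- clustered arm: 49 × [ICC/6 + (1 − ICC)(1 − r²)/53]
- unclustered arm: 49 × (1 − r²)/53

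Baseline adjustment reduces only the individual part, because group variance is taken to arise after baseline. Power comes from the noncentral t distribution, with 10 df (12 groups − 2) if both arms are clustered and Satterthwaite df if only the intervention arm is.

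Worked case, ICC 0.05 and r = 0.5:

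- Clustered arm: 49 × (0.00833 + 0.01344) = 1.067. Unclustered arm: 49 × 0.75/53 = 0.693.
- Both arms: SE = √(2 × 1.067) = 1.461; 3.99/1.461 = 2.73 on 10 df; power 0.69.
- Intervention arm only: SE = √(1.067 + 0.693) = 1.327; 3.99/1.327 = 3.01 on 13.1 df; power 0.79.

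| ICC (r = 0.5) | Both arms: power | Both arms: detectable increase | Intervention only: power | Intervention only: detectable increase |
|---|---|---|---|---|
| 0 | 0.86 | 13.8% | 0.89 | 13.1% |
| 0.02 | 0.79 | 15.2% | 0.85 | 13.9% |
| 0.05 | 0.69 | 17.1% | 0.79 | 15.1% |
| 0.10 | 0.57 | 19.8% | 0.70 | 16.9% |

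A simulation of the baseline-adjusted group-mean test (8,000 trials per setting, five groups of 9 and one of 8 per arm) gave 0.79, 0.70 and 0.58 (both arms) and 0.85, 0.79 and 0.70 (intervention only) at ICC 0.02, 0.05 and 0.10. Type I error was 0.049 to 0.057.

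**4. ICC at which power is exactly 80%.**

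| Case | Both arms | Intervention only |
|---|---|---|
| 53 per arm, r = 0.5 | 0.017 | 0.047 |
| 60 per arm (no attrition), r = 0.5 | 0.028 | 0.064 |
| 53 per arm, r = 0.7 | 0.046 | 0.090 |
| 53 per arm, r = 0.5, ordinary df (104) | 0.040 | 0.081 |
| 53 per arm, unadjusted, ordinary df | 0.01 | 0.02 |

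**5. Dependence on r and on the number of groups.** At ICC 0.05, moving r from 0.3 to 0.7 gives power 0.64 to 0.78 (both arms) or 0.735 to 0.89 (intervention only). Eight groups per arm with r = 0.5, which the wording in Section 2.3 would permit, give 0.76 and 0.84.

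**6. A test that ignores the groups.** At ICC 0.05 (40,000 simulated trials), a t-test rejects a true null in 9.6% of trials (both arms clustered) or 7.5% (intervention only). ANCOVA with r = 0.5 does so in 11.2% or 8.0%.

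**The case against.** The strongest reply is that no shortfall has been shown. Alpha, ICC, r and the degrees of freedom are all assumed, and at ICC 0.05 the results fall on both sides of 80%. That stands, and it limits what can be concluded.

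Part of the loss comes from the few-group degrees of freedom rather than from the ICC itself. This is also right: at r = 0.5 with both arms clustered, the 80% point is 0.040 on ordinary df and 0.017 on 10 df. At r = 0.3 the both-arms analysis has power 0.791 even at ICC 0. But with twelve groups, small-sample df are what a valid group-aware test needs, so their cost belongs in the power statement.

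An ICC requires groups to differ from one another, not merely to bond. A manual, one curriculum per arm and one- or two-day delivery all point to a modest value, and the MSCS also covers family, friends and organizations outside the group. This argues for the lower part of the range, but not for zero. With both arms clustered, 0.02 is already enough to bring power just below 80%.

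Snowball recruitment (Section 3.6) could make group members alike before baseline, so that adjustment removes some group variance. A model using the 1-, 4- and 10-month scores could also change power. Neither is quantified here, and the plan specifies neither adjustment nor such a model.

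Finally, Aim 3 is partly a pilot. That softens the consequence, but Aim 3b tests impact on the primary outcome and the plan chose to claim 80% power for it.

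**Conclusion.** The concern holds. Section 3.5 states a power that is right for independent participants, while the design delivers both arms in groups and the plan gives no ICC, design effect or between-arm MSCS model. With 53 per arm, six groups per arm, r = 0.5, small-sample df and two-sided alpha 0.05, the claim survives only up to an ICC of about 0.017 if both arms are clustered, or 0.047 if only the intervention arm is. At ICC 0.05 power is 0.69 or 0.79, and the increase detectable with 80% power is 17.1% or 15.1%.

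Confidence is high that the assumption is unstated and that the claim depends on it. The size of any shortfall is conditional on an ICC and a baseline correlation that the documents do not give. The plan does not propose a test that ignores the groups, so the type I error figures show why to rule one out, not an error already made. This should be fixed before analysis, but it does not call for a larger trial.

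**What to change.** Keep n=120.

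1. In Section 5.2.1, specify the between-arm MSCS comparison: a model adjusted for baseline MSCS, with a random effect for delivery group (in both arms, or in the intervention arm only if that is justified) and small-sample degrees of freedom. State that a comparison ignoring delivery group will not be used.
2. Restate Section 3.5 and Table 1 for that same analysis. Give alpha, the group structure, an ICC range (for example 0.02 to 0.10) and a baseline-correlation range (for example 0.3 to 0.7). Show the both-arms and intervention-arm-only cases, and give unadjusted figures only as a sensitivity case. The tables above can serve as the example.

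The cost is wording in Sections 3.5 and 5.2.1 and in Table 1, and possibly a less favourable stated detectable effect. No extra participants or new outcome data are needed, since MSCS is already collected at baseline. Delivery-group membership has to be kept in the analysis dataset.

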3.6 Enrollment

Phase I IDIs with YBMSM: We will recruit young men from the IDP clinic as well as from our CBO partners AID Atlanta, NAESM and Positive Impact. Recruitment will also include self-referral from email and social media announcements as well as posted flyers at community locations and within the clinic. Flyers and announcements will contain a link to an online screening survey as well as a telephone number to contact study staff. Interested individuals will be screened for eligibility criteria via phone or online survey (must be HIV-positive, biologically male, endorse sexual contact with men, and between the ages of 18 and 29). If eligible, study staff will then contact the participant to schedule an interview.

Phase I IDIs with Key Informants: We will directly contact clinic providers and CBO employees who we already know to be involved in work with YBMSM and offer participation in our study. We will also ask YBMSM in the initial qualitative interviews to nominate individuals from the community who they think could provide useful information. Finally, we will send email announcements to all of the IDP clinic and staff as well as listservs of the CBO partners, so that any additional interested individuals can self-refer into the study.

Phase II YCAB formation: Recruitment: Although YCAB members are not research participants, they will also be recruited as a part of the study. We will recruit YCAB members from a wide range of sources with the goal of retaining a diverse group of committed youth to advise us on our intervention development. Sources will include CBOs, our clinic site, and email advertisements to community listservs. As mentioned earlier, we will also specifically ask for recommendations from our key informants in the CBOs and healthcare settings. Eligible youth will be YBMSM ages 18-29 who are living with HIV, and we will attempt to have representation throughout this age range. We will choose 9 members for the YCAB based on diversity of age, experience, education, and

general interests. At the latest, we hope to complete this process by month 6 of the award period.

Phase III Randomized Controlled Trial: Recruitment: We will recruit YBMSM from the IDP clinic as well as from our CBO partners AID Atlanta, NAESM and Positive Impact. Community recruitment will occur via self-referral from email and social media announcements as well as posted flyers at community locations and within the clinic. When interested individuals contact the study team, they will be screened for eligibility criteria via phone or online survey. Of note, participants do not need to be patients at the IDP clinic; as long as they consent to release of medical records and chart abstraction by our study team, we will be able to obtain HIV related outcome data. If eligible, study staff will then contact the participant to schedule an interview. We will also directly contact and offer screening to patients in our clinic who meet the age criteria (aged 18-29), as long as the medical providers agree to the patients being directly approached at that time. The eligibility screening can be done in person, via phone or via an online survey. At other times, we will also pass out flyers and other promotional materials at events that may be likely to be frequented by YBMSM (e.g., Gay Pride festival), and we will consult with our YCAB for advice about such venues and events. We will also do on-site recruitment at the clinic and community venues/events, in which we will approach potential participants and ask if they are interested in completing an online screening survey for eligibility in our study. If yes, they will have the option to complete the survey on a tablet at that time. We will also use the snowball sampling method to recruit participants. After completing the intervention, we will distribute 5 flyers to each participant to distribute to people within their social networks as referrals to our program. These flyers will be marked with a number that is unique to each participant. If a potential participant contacts us through the referral method, they will provide the number marked on the flyer. These potential participants will then complete an online screening survey for eligibility in our study.

3.7 Consent Process: In order to screen potential participants for eligibility for the RCT, we will obtain online consent – this will be accompanied by a verbal consent discussion of the consent document if a staff member is present (e.g., at a community event or in the clinic), and will be online only if a participant is self-referring to the eligibility survey from a flyer or friend. For the RCT participants, we will obtain written consent. The consent form is attached and includes specific permission to access participants' medical records for the purposes of abstracting the clinical outcomes (Appendix B). We are requesting a waiver of written consent for the IDI participants (YBMSM as well as key informants) as their signing of the consent form would be the only written record of participation and therefore could increase potential for breach of confidentiality. There is precedent for such waivers in our prior research; furthermore, federal regulations state that the IRB may waive the requirement for written consent if this will be the only record linking the subject and the research, and the principal risk would be potential harm resulting from a breach of confidentiality (45 CFR 46.117(c)). We will obtain verbal consent using the scripts attached to this application (Appendix A). YCAB members will not consent as they are not technically research participants, but rather advisors to the research process.

3.8 Tokens of Appreciation:

In Phase I, participants (whether YBMSM or key informants) will receive \$50 cash or gift card for participating in in-depth interviews. Participants in the RCT will receive \$25 cash/gift card for the first intervention session and \$50 for the second intervention session. Also, they will receive \$25 for taking the social capital surveys at 4 months and 10 months after study completion (\$150 total). The subset who participate in post hoc qualitative interviews will receive an additional \$25 for that visit and therefore receive a total of \$175 over the course of 10 months participating in the study. Participants who refer up to 5 potential participants to the study will receive \$10 for each participant that enrolls in the study (Up to \$30). Additionally, MARTA cards (valued at \$5/round-trip) will be offered to all participants in all phases to enable them to get to the study sites and participate.

